IRB Minimal Risk Protocol Template

Note: If this study establishes a human specimen repository (biobank) for research purposes, do not use this template. Use the Mayo Clinic Human Specimen Repository Protocol Template found on the IRB home page under Forms and Procedures at <http://intranet.mayo.edu/charlie/irb/>

First-time Use: Use this template to describe your study for a new IRB submission.

1. Complete the questions that apply to your study.
2. Save an electronic copy of this protocol for future revisions.
3. When completing your IRBe application, you will be asked to upload this document to the protocol section.

Modification: To modify this document after your study has been approved:

1. Open your study in IRBe. Click on the study 'Documents' tab and select the most recent version of the protocol. Save it to your files.
2. Open the saved document and activate "Track Changes".
3. Revise the protocol template to reflect the modification points , save the template to your files
4. Create an IRBe Modification for the study and upload the revised protocol template.

General Study Information

Principal Investigator: [name]

Co-investigators: [name], [name]

Study Title: Paravertebral block vs no block in open pancreaticoduodenectomy: prospective randomized controlled trial
NCT05820997

Protocol version number and date: V1 11/2/2022, V3 1/17/2023

Research Question and Aims

Hypothesis: We hypothesize that patients undergoing open pancreaticoduodenectomy who receive a paravertebral block, will have less postoperative pain and a shorter length of stay than those who only receive no paravertebral block.

Aims, purpose, or objectives:

Compare intra and postoperative pain control between Paravertebral block vs no block in open pancreaticoduodenectomy. Length of stay, and complications will also be recorded.

Background (Include relevant experience, gaps in current knowledge, preliminary data, etc.):

Pancreaticoduodenectomy (PD) is the surgical procedure of choice for the resectable and the borderline pancreatic cancers as well as many other indications [1]. Much progress has been attained in order to improve outcomes, such as length of hospital stay, pain management, and complications after PD [2]. Postoperative pain is one of the most frequent complaints after open pancreaticoduodenectomy. For that reason, different surgical approaches have been implemented to decrease the intra and postoperative pain such as changing the skin incision from subcostal transverse to upper midline small incision, epidural catheter use, or even minimally invasive surgery. Multimodal analgesic techniques play an important role in this particular field.

The para vertebral block (PVB) is a regional anesthesia technique which is widely used in thoracic surgeries[3]. PVB has been described mainly for ipsilateral somatic and sympathetic nerve blockade in multiple contiguous dermatomes above and below the site of injection[4]. Most literatures show its efficacy in pain management for thoracic surgeries and more recently PVB has been recommended and used for a wide range of abdominal surgeries, such as inguinal hernia repair and appendectomy[5].

Although, thoracic PVB have been performed for abdominal procedures[6], there is no enough knowledge data about the effect of PVB on the outcome of complex abdominal surgeries, such as open PD [2, 7]. For that reason, we aim to compare intra and postoperative pain management between PVB versus no block in open PD.

Study Design and Methods

Methods: Describe in lay terms, completely detailing the research activities that will be conducted by Mayo Clinic staff under this protocol.

Paravertebral block is one of the standard of care options for postoperative pain management in patients with under going open pancreaticoduodenectomy.

Patients scheduled for surgery will be randomized into two groups through simple open randomization. Randomization and data capture will be done using the REDCap system. Patients in group A, will receive a paravertebral block, administered preoperatively, which is standard of care. Those in group B will form a control group receiving no paravertebral block, which is standard of care. For the Paravertebral Block group; patients will receive an ultrasound guided paravertebral at the T7-10 levels bilaterally with 5 cc of .5% ropivacaine at each level. The ropivacaine is given as a local anesthetic. Intraoperative analgesic management will be at the discretion of the anesthesiologist. Currently receiving the block pre-procedure is standard of care and not receiving the block is standard of care and given based on physician assessment. For this study we would plan to randomize to obtain objective data for clinical decisions and improve patient outcomes between the two standard of care groups. Patients would normally be in one or the other group even if they do not participate in the study. With the randomization we hope to obtain more objective data regarding patient outcomes.

Following surgery patients in both groups, we will collect data from the first 48 hours after surgery and at discharge. Patients will not be required to come into the clinic for any extra visits, there will be no questionnaires.

Study design: Prospective, Randomized Trial

Subject Information

Target accrual is the proposed total number of subjects to be included in this study at Mayo Clinic. A "Subject" may include medical records, images, or specimens generated at Mayo Clinic and/or received from external sources.

Target accrual: 40

Subject population (children, adults, groups): Adults

Inclusion Criteria:

- Patients willing and have signed consent.
- Nonpregnant adults undergoing open pancreaticoduodenectomy via standard upper midline incision without contraindications to PVB

Exclusion Criteria:

- Not able or unwilling to sign consent.
- Currently pregnant or lactating.
- Patients with chronic pain, requiring daily opiate use at time of surgery.
- Patients intolerant of opiates, NSAIDS, acetaminophen or local anesthetics.

Biospecimens

Collection of blood samples. When multiple groups are involved copy and paste the appropriate section below for example repeat section b when drawing blood from children and adults with cancer.

a. **From healthy, non-pregnant, adult subjects who weigh at least 110 pounds.** For a minimal risk application, the amount of blood drawn from these subjects may not exceed 550ml in an 8 week period and collection may not occur more frequently than 2 times per week.

Volume per blood draw: _____ ml

Frequency of blood draw (e.g. single draw, time(s) per week, per year, etc.) _____

b. **From other adults and children considering age, weight, and health of subject.** For a minimal risk application, the amount of blood drawn from these subjects may not exceed the lesser of 50 ml or 3 ml per kg in an 8 week period, and collection may not occur more frequently than 2 times per week.

Volume per blood draw: _____ ml

Frequency of blood draw (e.g. single draw, time(s) per week, per year, etc.) _____

Prospective collection of biological specimens other than blood: _____

Review of medical records, images, specimens

Check all that apply (data includes medical records, images, specimens).

Only data that exists before the IRB submission date will be collected.

Date Range for Specimens and/or Review of Medical Records:

Examples: 01/01/1999 through 12/31/2015, or all records through mm/dd/yyyy.

Note: The Date Range must include the period for collection of baseline data, as well as follow-up data, if applicable.

The study involves data that exist at the time of IRB submission **and** data that will be generated after IRB submission. Include this activity in the Methods section.

Examples

- The study plans to conduct a retrospective chart review and ask subjects to complete a questionnaire.
- The study plans to include subjects previously diagnosed with a specific disease and add newly diagnosed subjects in the future.

The study will use data that have been collected under another IRB protocol. Include in the Methods section and enter the IRB number from which the research material will be obtained. *When appropriate, note when subjects have provided consent for future use of their data and/or specimens as described in this protocol.*

Enter one IRB number per line, add more lines as needed

Data Specimens Data & Specimens _____

Data Specimens Data & Specimens _____

Data Specimens Data & Specimens _____

Data Analysis

Power analyses may not be appropriate if this is a feasibility or pilot study, but end-point analysis plans are always appropriate even if only exploratory. Provide all information requested below, or provide justification if not including all of the information.

Power Statement:

The primary endpoint is postop pain visual analog scale. With pain scale ranging from 0 to 10, the standard deviation is estimated to be 2.5, based on two-sample t test, 20 patients per group (40 in total) will allow us to detect a mean difference of 2 points or larger in postop pain scale, with 0.05 significance level and 80% power.

Data Analysis Plan:

Patients demographic and baseline characteristics will be summarized as mean (SD) or median (range) for continuous variables and frequency (%) for categorical variables. Standardized mean difference will be calculated to indicate the size of the difference between the randomized groups. Postop outcome variables will be reported as mean (SD) or median (range) for continuous variables and frequency (%) for categorical variables. Two-sample t test will Wilcoxon rank sum test will be used to compare continuous variables between the two groups and chi-squared test or Fisher's exact test will be carried out to compare the categorical variables. All tests will be two-sided, with p value<0.05 considered statistically significant.

Endpoints

Primary:

Intra and postoperative pain medications consumption

Mean pain score initial 48 hrs postop

Length of stay

Return of bowel function

Secondary: Postop complications

References:

- Tempero, M.A., et al., *Pancreatic adenocarcinoma, version 2.2014: featured updates to the NCCN guidelines*. J Natl Compr Canc Netw, 2014. **12**(8): p. 1083-93.
2. Karim, S.A.M., et al., *The outcomes and complications of pancreaticoduodenectomy (Whipple procedure): Cross sectional study*. Int J Surg, 2018. **52**: p. 383-387.
3. Pawa, A., et al., *Paravertebral Blocks: Anatomical, Practical, and Future Concepts*. Current Anesthesiology Reports, 2019. **9**(3): p. 263-270.
4. Karmakar, Manoj K., *Thoracic Paravertebral Block*. Anesthesiology, 2001. **95**(3): p. 771-780.
5. Page, E.A. and K.L. Taylor, *Paravertebral block in paediatric abdominal surgery-a systematic review and meta-analysis of randomized trials*. Br J Anaesth, 2017. **118**(2): p. 159-166.
6. Novak-Janković, V. and J. Marković-Božić, *REGIONAL ANAESTHESIA IN THORACIC AND ABDOMINAL SURGERY*. Acta Clin Croat, 2019. **58**(Suppl 1): p. 96-100.

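### The Power Statement names one primary endpoint and the Endpoints section lists four, all tested at p<0.05 with no rule for what makes the trial positive

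*Combined protocol and SAP*

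**What the plan says.** In the Data Analysis part of the combined protocol and SAP, the Power Statement uses the singular: "The primary endpoint is postop pain visual analog scale". It sizes the trial on that endpoint alone, stating that "20 patients per group (40 in total) will allow us to detect a mean difference of 2 points or larger in postop pain scale". It gives no time point for the pain score.

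The Endpoints section has four entries under its Primary label:

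- "Intra and postoperative pain medications consumption"
- "Mean pain score initial 48 hrs postop"
- length of stay
- "Return of bowel function"

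Postoperative complications are the only secondary endpoint. The Data Analysis Plan applies one threshold throughout: "All tests will be two-sided, with p value<0.05 considered statistically significant".

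Research Question and Aims does not settle which account is meant. The hypothesis is that patients given the block "will have less postoperative pain and a shorter length of stay", which puts length of stay on a level with pain. The aims lead with pain control and add that "Length of stay, and complications will also be recorded".

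**The concern.** The two accounts of the primary endpoint cannot both govern, and nothing ranks one above the other. No section gives an order of testing, a division of alpha, a co-primary rule or a definition of a positive trial. The deciding result can therefore be chosen after the data have been seen.

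Two things are at stake. First, if one significant result out of four is enough for a positive conclusion, the 0.05 level holds for each test but not for the conclusion. Second, a primary claim could rest on medication use, length of stay or bowel function, for which the plan gives no sample-size basis. Return of bowel function is not even defined as a time or a yes/no outcome.

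**Working it through.** **Inputs from the documents.** Four listed primaries (Endpoints); two-sided 0.05 for each test (Data Analysis Plan); 20 per group, difference 2 points, SD 2.5, stated power 80% (Power Statement). The documents give no correlations between endpoints and no event rate for bowel function, so the values used below are assumptions.

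**1. The plan's own figure.** For a two-sample t test the noncentrality is 2 / (2.5 × √(2/20)) = 2.53 with 38 degrees of freedom.

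| Test at 0.05, 20 per group | Noncentral t | Normal approximation |
|---|---|---|
| Two-sided | 69.3% | 71.6% |
| One-sided | 79.9% | 81.2% |

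The stated 80% is not reproduced under the plan's two-sided testing; only a one-sided test matches it. Two-sided 80% power needs 26 per group by the t test. This is a separate problem, and the error rates below do not depend on it.

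**2. Error rate under each possible success rule**, when the block affects none of the four endpoints:

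- *Pain score alone decides:* 5%.
- *All four must be significant:* at most 5%. In simulation it was 0.1% at a common correlation of 0.5 and 1.8% at 0.9.
- *Any one is enough, independent tests:* 1 − (1 − 0.05)^4 = 1 − 0.8145 = 0.1855, or 18.5%.

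**3. Any-one rule with correlated endpoints.** Simulation of 200,000 null trials per setting, 20 per group, equally correlated normal endpoints, two-sided t tests at 0.05 (Monte Carlo standard error below 0.001):

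| Assumed correlation | 0 | 0.3 | 0.5 | 0.7 | 0.9 |
|---|---|---|---|---|---|
| Four tests | 18.5% | 17.4% | 15.7% | 13.2% | 9.4% |
| Five tests | 22.6% | 21.0% | 18.3% | 15.0% | 10.3% |

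The five-test row applies if intraoperative and postoperative medication use are tested separately: 1 − 0.95^5 = 0.226 for independent tests.

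**4. Upper bound.** With one test per endpoint, each of size at most 0.05, the Bonferroni bound is 4 × 0.05 = 20%, whatever the correlations.

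**5. If return of bowel function is yes/no.** The other three endpoints are taken as independent t tests, with assumed event rates of 10% to 90%:

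- Fisher's exact test has size 0.012 to 0.025 at 20 per group. The overall rate is 1 − 0.95^3 × (1 − size), which is 15.3% to 16.4%.
- The uncorrected chi-squared test, which the plan equally allows, has size 0.039 to 0.053. The overall rate is 17.6% to 18.8%.

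**6. Keeping four primaries with Bonferroni.** Each is tested at 0.05/4 = 0.0125. The familywise rate is 1 − 0.9875^4 = 4.9% for independent tests. Power for the 2-point pain difference with 20 per group falls to 47%, and about 37 per group would be needed for 80% (t test).

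**The case against.** The strongest reply is that no section says one significant result is enough. The sentence that sets the sample size names a single endpoint, and on that reading the error rate is 5%. The hypothesis joins pain and length of stay with an *and*, which does not suggest an any-one rule. This stands to the extent that the inflation is conditional; what is certain is the contradiction and the missing rule. It does not remove the problem, because nothing places the Power Statement above the Endpoints section, and the hypothesis covers two of the four listed primaries without attaching a decision rule.

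It can also be said that independence is implausible: pain scores and analgesic use come from the same patients over overlapping periods, and bowel function and length of stay are plausibly linked to them. That is fair, and 18.5% is near the upper end for four single tests. Under an any-one rule, however, the rate is still 9.4% at a correlation of 0.9.

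The 20% bound also needs a qualification. It assumes one test per endpoint of size at most 0.05, while the sentence naming the t and Wilcoxon tests is garbled and does not fix which applies. If significance on either counted, the error per endpoint would be about 6.3% for normal data, or 1 − 0.937^4, about 23%, over four independent endpoints. An uncorrected chi-squared test of size 5.3% for one endpoint would move the bound to about 20.3%. Both points make the problem slightly larger.

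Finally, other remedies would also resolve the contradiction, such as co-primaries with a stated rule or Holm across all four. That is true, but an all-four rule or a split of alpha lowers power further in a trial of 40.

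**Conclusion.** The point holds and should be corrected. The plan contradicts itself on the primary endpoint and gives no rule for a positive trial. If any one of four significant primaries counts, the false-positive rate is 18.5% for independent tests and about 9% to 17% at assumed common correlations of 0.9 down to 0.3. It stays within 20% provided each endpoint has one test of size at most 0.05. If the Power Statement governs, or if all four must succeed, there is no inflation. The documents do not say which rule applies, and that omission is the defect. The shortfall in power (69% against the stated 80%) is real but has a different cause and adds no weight here.

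**What to change.** Before outcome data are examined:

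1. Make the mean pain score over the first 48 hours the single primary endpoint, tested by the two-sample t test at two-sided 0.05. It is the listed item closest to the powered pain scale. That match is an assumption, because the Power Statement gives no time point, so the Power Statement should be reworded to name the same endpoint.
2. Move medication consumption, length of stay and return of bowel function to secondary. Say whether intraoperative and postoperative medication use form one variable or two, and whether bowel function is a time or a yes/no outcome. Name one suitable test for each.
3. Test these secondaries only if the primary is significant, in a pre-stated fixed order or with Holm. Alternatively, label them exploratory and make no significance claim.

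The cost is wording in the Power Statement, Endpoints and Data Analysis Plan sections. The sponsor gives up calling three endpoints primary. No patients or data collection change. The error rate of the primary conclusion returns to 5%, but power stays at 69% with 20 per group, so the sample size must be dealt with separately.

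### The stated 80% power is wrong: with the planned two-sided test, 20 per group gives about 69% power for a 2-point difference, and with the stated inputs 80% needs a one-sided 0.05 test

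*Combined protocol and SAP*

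**What the plan says.** The Power Statement, under Data Analysis in the combined protocol and SAP, names the postoperative pain score on a 0 to 10 scale as the primary endpoint. It gives these inputs:

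- Variability: "the standard deviation is estimated to be 2.5".
- Test, sample size and difference: a two-sample t test, and "20 patients per group (40 in total) will allow us to detect a mean difference of 2 points or larger in postop pain scale".
- Error rates: "with 0.05 significance level and 80% power". It does not say whether the 0.05 is one-sided or two-sided.

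The Data Analysis Plan that follows settles the sidedness: "All tests will be two-sided, with p value<0.05 considered statistically significant".

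Subject Information gives "Target accrual: 40", the same total as in the power calculation.

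**The concern.** A 2-point difference with an SD of 2.5 is a standardised effect of 2/2.5 = 0.8. For that effect, 20 per group is too few for 80% power in a two-sided t test at 0.05. Either the Power Statement describes a test that the trial will not run, or its arithmetic is wrong.

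This sentence is the protocol's only justification for enrolling 40 patients. Anyone relying on it believes the trial has a one-in-five chance of missing a 2-point benefit. If the real chance is nearer one in three, a non-significant result is weaker evidence against the block than it will appear. The trial is meant to inform the choice between two options that are both standard of care, so a null result is likely to be used.

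**Working it through.** **Inputs, all from the protocol.** Difference d = 2, SD s = 2.5, n = 20 per group, two-sample t test and alpha = 0.05 (Power Statement); two-sided testing (Data Analysis Plan); total of 40 (Subject Information).

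**Formula.** Under the alternative, the t statistic has a noncentral t distribution with 2n − 2 degrees of freedom and noncentrality d / (s × √(2/n)).

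- Degrees of freedom: 2 × 20 − 2 = 38.
- Noncentrality: 2 / (2.5 × √(2/20)) = 2 / 0.7906 = 2.53.

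**Trying to reproduce the stated 80%.**

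| Calculation, 20 per group | Critical t | Power, exact t | Power, normal approximation |
|---|---|---|---|
| Two-sided 0.05, as planned | 2.024 | 69.3% | 71.6% |
| One-sided 0.05 | 1.686 | 79.9% | 81.2% |

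A simulation of 20,000 trials with the two-sided t test gave 69.4%, so the shortfall does not come from the choice of formula.

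The normal-approximation sample size points the same way. The formula is n = 2 × (z for alpha + z for power)² × s² / d².

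- One-sided: 2 × (1.645 + 0.842)² × 6.25 / 4 = 19.3, rounded up to 20 per group. This is the protocol's figure.
- Two-sided: 2 × (1.960 + 0.842)² × 6.25 / 4 = 24.5, rounded up to 25 per group.

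A one-sample or paired formula with n = 20 gives about 92%, so it does not explain the stated figure.

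**What the planned two-sided test delivers (exact t).**

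- Chance of missing a true 2-point difference: 100% − 69.3% = 30.7%, against the implied 20%.
- Difference detectable with 80% power at 20 per group: 2.27 points.
- Sample size for 80% power at 2 points: 26 per group (80.7%), or 52 in total; 25 per group gives 79.1%.
- SD at which 20 per group would give 80% power for 2 points: 2.20, against the stated 2.5.

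**Departures from 20 evaluable patients per group.** The protocol gives no rate of non-evaluable patients, so the first two rows are assumptions that show a range.

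| Scenario | Two-sided power for 2 points |
|---|---|
| 18 per group (10% not evaluable, assumed) | 64.5% |
| 16 per group (20% not evaluable, assumed) | 59.1% |
| All 40 evaluable, split 16/24 | 67.6% |
| 20 per group, Wilcoxon test, normal data (simulated) | about 67% |

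**The case against.** The strongest reply is that 69% is the power for the stated inputs and not necessarily for the analysis that will be done. The Power Statement applies the SD of 2.5 to a postoperative pain score, while the Endpoints section lists the mean score over the first 48 hours. The protocol does not say which of the two the SD describes. If 2.5 is the SD of a single reading, averaging repeated readings would lower it. For example, assuming four to twelve equally correlated readings with a correlation of about 0.70 to 0.75, the SD would fall to near 2.2, and two-sided power would be about 80%. This stands as a caveat: the 31% miss rate is conditional on 2.5 being the SD of the analysed endpoint. It does not rescue the sentence, which makes its claim at 2.5.

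It is also fair to say that the one-sided explanation is inferred from the arithmetic. The protocol never states it. The error does not depend on the explanation, because 80% fails under the protocol's own two-sided rule.

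The loss-of-data scenarios are illustrative. Data come from the hospital stay, with no extra visits or questionnaires, so losses may be small. The shortfall from 80% to 69% is there with no losses at all.

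Finally, the repair need not be wording alone. The protocol does not say whether 2.0 or 2.3 points is the difference that matters, so whether to enrol more patients is for the sponsor to decide.

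**Conclusion.** The concern holds. With the protocol's own inputs and its two-sided rule, power for a 2-point difference is 69.3%, about 11 percentage points below the stated 80%. The chance of missing that difference is about half as large again as stated (30.7/20 = 1.5). At those inputs, 80% is reached with a one-sided 0.05 test, which the analysis plan excludes.

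The figures assume an SD of 2.5 for the endpoint analysed, normal data, a t test, and 20 evaluable patients in each group. Missing data, unequal groups under simple randomisation, or use of the Wilcoxon test would each lower power somewhat further. The error flatters the design and bears on the sample-size rationale, so it must be corrected.

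**What to change.** Reword the Power Statement to agree with the two-sided plan, for example:

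> With an SD of 2.5, 20 evaluable patients per group give 69% power to detect a difference of 2 points, and 80% power to detect 2.3 points, using a two-sided two-sample t test at the 0.05 level. These figures assume that all 40 patients are evaluable and equally divided between the groups.

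It would help to state in the same place whether 2.5 is the SD of a single score or of the 48-hour mean.

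The cost is protocol wording only: no new procedures or data, and no change in accrual is needed to make the statement true. The price is a less favourable figure. If the sponsor wants to keep 80% power for 2 points, the target becomes 26 evaluable patients per group, 52 in total, which is 52 − 40 = 12 more than now, plus any allowance for missing data. A one-sided test would need an explicit justification and a matching change to the Data Analysis Plan.

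### Should the plan name baseline variables to adjust the 48-hour pain comparison, given 40 patients under simple randomisation?

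*Combined protocol and SAP*

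**What the plan says.** The Methods text under Study Design and Methods sets the allocation: "Patients scheduled for surgery will be randomized into two groups through simple open randomization". It mentions no blocking or stratification. Subject Information gives "Target accrual: 40", and the Power Statement assumes an even split of 20 and 20.

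The Data Analysis Plan treats baseline data descriptively: "Patients demographic and baseline characteristics will be summarized", and "Standardized mean difference will be calculated to indicate the size of the difference between the randomized groups". For continuous outcomes, which include the listed endpoint "Mean pain score initial 48 hrs postop", it says "Two-sample t test will Wilcoxon rank sum test will be used to compare continuous variables between the two groups". A connecting word is evidently missing between the two test names. Both tests are unadjusted.

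The document contains no regression model, no list of covariates and no rule tied to the size of an SMD. It names no individual baseline variable. Methods adds that "there will be no questionnaires", so a preoperative pain score cannot be taken for granted.

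**The concern.** A plan that measures imbalance without saying what follows from it seems to stop half-way. With about 20 patients per group, a sizeable difference on some baseline variable is likely. If that variable predicts pain, the observed pain difference in that particular trial is shifted, and the SMD table will show readers why. The result might then be disputed, or someone might adjust after seeing the data and choose the covariate to suit. An analysis of covariance fixed in advance would close that route. It would also use prognostic information to narrow the confidence interval, which matters in a trial this small.

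**Working it through.** **Inputs.** From the Power Statement: SD 2.5, difference 2 points, 20 per group, significance level 0.05, stated power 80%. From the Data Analysis Plan: two-sided tests. Assumed, because the documents give none: the correlation r between a baseline covariate and the pain score (multiple correlation R for two covariates), taken over 0 to 0.5.

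**1. The plan's own figure.** The noncentrality is 2 / (2.5 × √(1/20 + 1/20)) = 2.530. With 38 degrees of freedom and a two-sided critical value of 2.024, power is **69.3%**. One-sided, it is 79.9%, close to the stated 80%. That mismatch with two-sided testing is a separate point. Here 69.3% is the baseline for comparison.

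**2. Validity of the unadjusted test.** In 20,000 simulated trials per scenario (r = 0, 0.3, 0.5, 0.6), the unadjusted t test rejected a true null in 4.8% to 5.2% of trials and the adjusted model in 4.8% to 5.0%. Leaving the covariate out does no harm to the error rate.

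**3. Precision gained by adjustment.** With k covariates the residual SD is 2.5 × √(1 − R²), the degrees of freedom are 38 − k, and chance covariate imbalance inflates the variance of the treatment difference by 1 + k/(37 − k). For k = 1 and r = 0.3, the SD is 2.385, the inflation is 1.028, and the noncentrality is 2 / (2.385 × √(0.1 × 1.028)) = 2.616, so power is 72.2%.

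| r (or R) | One covariate | Two covariates |
|---|---|---|
| 0 | 68.1% | 66.8% |
| 0.2 | 69.9% | 68.6% |
| 0.3 | 72.2% | 70.9% |
| 0.4 | 75.5% | 74.3% |
| 0.5 | 80.1% | 79.0% |
| Unadjusted | 69.3% | 69.3% |

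Break-even is r ≈ 0.17 for one covariate and R ≈ 0.24 for two. At r = 0.2 the gain is 69.9 − 69.3 = 0.6 points. A covariate unrelated to pain costs 69.3 − 68.1 = 1.2 points.

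**4. How often imbalance appears, and what it does.** For one continuous variable, P(|SMD| > 0.5) = 2 × P(t₃₈ > 0.5/√(2/20)) = 12.2%. At an SMD of exactly 0.5 the unadjusted pain difference moves by r × 2.5 × 0.5, which is 0.25 points at r = 0.2 and 0.63 at r = 0.5. Given that imbalance, power for a true 2-point difference is 58% (r = 0.2) down to 38% (r = 0.5) if it works against the block, and 79% up to 93% if it favours it. These are conditional figures. Over all 20/20 allocations the power is the 69.3% of step 1.

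**5. Whether one named covariate settles the matter.** Taking variables as independent, the chance that at least one of five shows |SMD| > 0.5 is 1 − (1 − 0.122)⁵ ≈ 48%; for ten it is 1 − (1 − 0.122)¹⁰ ≈ 73%. Adjusting for one leaves the rest visible and unadjusted.

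**6. Unequal group sizes.** Simple randomisation gives exactly 20/20 in 12.5% of trials. Averaged over the possible splits, unadjusted power is 68.2%, so unequal splits cost about 1 point.

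**The case for a change.** The best argument for a change concerns pre-specification more than power. The SMD table will expose imbalance, and no sentence forbids acting on it. In an illustrative worst case (three to five independent covariates, each with r of 0.2 to 0.3, and the smallest p-value taken from the unadjusted and single-covariate analyses), the type I error rises from 5% to about 8% to 11%. Writing a rule beforehand costs one paragraph and no patients. If a strongly prognostic variable were available, with r of 0.4 or more, the gain of about 6 points or more would be worth having.

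Part of this stands: the plan does not say outright that SMDs trigger no adjustment, and an adjusted analysis is a respectable alternative. But the worst case requires an analyst to leave the plan, which gives the SMD a descriptive purpose and then names only unadjusted tests. An adjusted result produced later would be recognisable as a departure. Nor does the document support a strong correlation. It names no candidate variable, provides for no questionnaires, and excludes patients with chronic pain who need daily opiates, which removes one likely source of variation in pain. A model with its covariate left blank is not a change the sponsor could adopt.

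**Conclusion.** No change is needed. Unadjusted comparison is a legitimate primary analysis for a randomised trial, and here it holds its error rate. The case for adjustment rests on an assumed correlation. It loses 1.2 points of power if the covariate is useless, gains 0.6 at r = 0.2 and 2.9 at r = 0.3 (72.2 − 69.3), and reaches the stated 80% only at r of about 0.5. It would not end argument over imbalance in the remaining variables.

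Stating that the SMDs are descriptive would record what the Data Analysis Plan already implies, and analysts following it would act that way regardless. Blocking would recover about 1 point at the price of a more predictable allocation in an open trial, which is a fair trade-off to decline.

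The conclusion assumes the plan's SD of 2.5 and 2-point difference, normally distributed scores and, for the adjusted figures, a 20/20 split. It would be worth reopening if, before outcome data are examined, the sponsor could name a variable recorded for every patient and expected to correlate with pain at about 0.4 or more.
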